## **3.2 Study Duration, Enrollment and Number of Sites**

### **3.2.1 Duration of Study Participation**

The study duration per subject will be up to 2 years, with up to 1 day of screening and baseline assessment, up to 1.5 years of Intervention visits, and 6 months follow-up.

### **3.2.2 Total Number of Study Sites/Total Number of Subjects Projected**

The study will be conducted at 2 investigative sites in the United States. The Children's Hospital of Philadelphia, and The New York Blood Center (no subject enrollment, providing *RH* genotyped red cell units and engaged in research activities).

Recruitment will stop when approximately 20 subjects are enrolled. It is expected that approximately 20 subjects will be enrolled to produce 18 evaluable subjects.

## **3.3 Study Population**

We will enroll at least 5 adults to collect safety and preliminary efficacy data, before enrolling children to the study

### **3.3.1 Inclusion Criteria**

- 1) Males or females age  $\geq$  8 years.
- 2) Diagnosis of SCD, all genotypes
- 3) Requires chronic red cell transfusion therapy
- 4) Requires a minimum of 3 units per transfusion visit

---

- 5) History of anti-D
- 6) *RH* genotype predicts D+ expression
- 7) Anti-D not detectable at screening visit and past 6 months

### **3.3.2 Exclusion Criteria**

- 1) Rare *RH* genotype that would preclude sufficient RBC units
- 2) Antigen negative requirements due to alloimmunization that would preclude sufficient RBC units
- 3) Parents/guardians or subjects who, in the opinion of the Investigator, may be non-compliant with study schedules or procedures.

Subjects that do not meet all of the enrollment criteria may not be enrolled. Any violations of these criteria must be reported in accordance with IRB Policies and Procedures.

For subjects with a history of stroke/recurrent transient ischemic attack or other indication who require tight control of Hb S and *RH* genotyped blood is not available, standard of care serologic matched blood would be administered rather than delaying transfusion and risking higher Hb S level.

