## 1 BACKGROUND INFORMATION AND RATIONALE

### 1.1 Introduction

Red blood cell transfusion remains a life-saving therapy for patients with sickle cell disease (SCD). A major problem is the high rate of alloimmunization (antibody formation against transfused red cells) that occurs in transfused patients with SCD. Alloimmunization leads to delays in care, increases costs, and makes transfusion therapy unsafe and impossible for some patients. The most common antibodies formed by patients with SCD are directed against the Rh blood group system. Genetic diversity in Rh antigens in patients and blood donors of African descent contributes to the high incidence and complexity of antibodies found in patients with SCD. Recent studies performed by our group and others demonstrate *RH* genetic variants in patients and donors is a major risk factor leading to Rh alloimmunization. Routine blood bank assays cannot identify these variants, so although Rh-matched red cells by standard serologic assays are transfused to patients with SCD, they would only be truly Rh-matched with DNA-based matching. Many D+ patients have formed anti-D, and now require D- units, resulting in new challenges. These anti-D suggest exposure to different or variant D protein on donor cells. The major goal of this study is to perform pilot clinical studies to test whether providing *RH* genotype matched D+ RBCs to chronically transfused patients with SCD and anti-D is feasible, safe, and can lessen demand for D- RBC units. *RH* genotype matched red cells are not currently available for transfusion outside this study except for rare cases. We will determine the feasibility of identifying adequate genotype matched donor units in real clinical practice, identify barriers, and prospectively monitor patients for anti-D reappearance or signs of hemolysis.

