### **2.1 Primary Objective**

The primary objective of this study is to determine the feasibility and safety of *RH* genotype matched red cells (intervention) for chronically transfused D+ patients with SCD and history of anti-D. We will determine whether sufficient *RHD* genotyped units can be matched to the patient's own *RH* genotype, and whether re-exposure to D+ units that are *RHD* genotype matched is safe, as monitored by anti-D reappearance or signs of hemolysis.

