### 6.1 Primary Endpoint

The primary endpoint is the feasibility and safety of providing *RH* genotype matched D+ red cells for patients with SCD and history of anti-D who require chronic transfusion. *RH* genotype matched red cells are currently not available clinically except for rare circumstances. Descriptive, qualitative data, i.e. anti-D reappearance and signs and symptoms of increased red cell hemolysis, or delays in transfusion, will be collected to inform future multi-center studies of *RH* genotype matched red cells designed to test the effectiveness of providing *RH* genotype matched D+ red cells for patients with SCD and history of anti-D.

Given that there is donor center scalability with *RH* genotyping if more than one institution was requesting *RH* genotype matched red cells, we would consider this matching strategy feasible if provision of matched units were possible in > 85% of the transfusion study visits without a delay in transfusion.

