## **9.4 Recruitment Strategy**

Patients will be recruited from the chronic transfusion program for SCD at the Children's Hospital of Philadelphia. This will primarily include patients who receive their red cell transfusions erythrocytapheresis in the Apheresis Unit, but could include patients transfused by simple transfusion in the Day Hospital. Since the principal investigator is a pediatric hematologist and transfusion medicine specialist, she will refer her own patients as well as other care providers. All patients with SCD receiving chronic transfusion therapy will be screened for eligibility. If the prospective subjects are not patients of the investigator, one of the investigators or the research coordinator will approach the subjects and offer participation in the study in person during a transfusion visit. If recruitment is poor from the apheresis transfusion cohort at CHOP, patients receiving 2-3 units for simple red cell transfusion can be recruited from the Day Hospital.

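### Section 3.3.2 items 1 and 2 select patients on unit supply, so the >85% feasibility verdict is conditional on a supply pre-screen and biased upward for the stated population

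*Combined protocol and SAP*

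**What the plan says.** The feasibility question in section 2.1 is: "We will determine whether sufficient *RHD* genotyped units can be matched to the patient's own *RH* genotype". Section 1.1 sets it in routine care, aiming to determine "the feasibility of identifying adequate genotype matched donor units in real clinical practice, identify barriers".

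Section 3.3.2 (and the synopsis) then excludes on the same quantity. Item 1 is "Rare *RH* genotype that would preclude sufficient RBC units" and item 2 is "Antigen negative requirements due to alloimmunization that would preclude sufficient RBC units". Neither *rare* nor *sufficient* is given a cut-off.

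Section 6.1 sets the decision rule: "we would consider this matching strategy feasible if provision of matched units were possible in > 85% of the transfusion study visits", with no delay in transfusion. It adds that the data are to inform later multi-center studies. Section 6.2.2 makes timely issue of units a primary endpoint, summarized descriptively.

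Section 9.4 states: "All patients with SCD receiving chronic transfusion therapy will be screened for eligibility". No section says that patients turned away under items 1 or 2 will be counted, described or analysed.

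**The concern.** The entry filter and the endpoint are the same variable, namely whether enough suitable units exist for this patient. A patient foreseen to be hard to supply is removed before counting starts and adds no visit to the >85% denominator. This goes further than ordinary limited generalizability, because selection acts directly on the outcome and in the favourable direction. It would remain even if no enrolled subject were ever stopped early.

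The decision on whether the strategy is feasible is at stake. Section 6.1 states the verdict for the matching strategy as a whole. Sections 2.1 and 6.1 name the population as D+ patients with SCD and a history of anti-D who need chronic transfusion. A multi-center study planned from the figure would inherit a supply rate that leaves out the patients already judged hardest to supply. The hope in section 1.1 of easing demand for D- units also depends on what share of patients can be supplied at all.

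**Working it through.** **What can be reproduced.** The 85% threshold is not derived from any error rate, power or expected rate, so there is no calculation behind it to repeat. The enrolment figures are consistent: 18 evaluable of 20 enrolled (section 3.2.2) implies a 10% loss, since 18/0.90 = 20. The source pool in section 6.3 is 20-25 active patients plus 2-3 a year for 5 years, that is 20 + 10 = 30 to 25 + 15 = 40.

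**Inputs.**
- Enrolled: 20 (sections 3.2.2 and 6.3).
- Criterion: more than 85% of study visits (section 6.1).
- r, the observed share of visits supplied among enrolled subjects: assumed 90%, 95% or 100%.
- x, the number of otherwise eligible patients excluded under items 1 or 2: not in the documents; assumed 1 to 5, extended to 6 in one check.
- q, the share of visits at which an excluded patient could have been supplied: assumed 0, then 30%.
- Equal visits per patient: assumed.

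**Formula.** Rate with supply-excluded patients restored = (20r + xq)/(20 + x).

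**Results with q = 0:**

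| Observed r | x = 1 | x = 2 | x = 3 | x = 4 | x = 5 |
|---|---|---|---|---|---|
| 90% | 85.7% | 81.8% | 78.3% | 75.0% | 72.0% |
| 95% | 90.5% | 86.4% | 82.6% | 79.2% | 76.0% |
| 100% | 95.2% | 90.9% | 87.0% | 83.3% | 80.0% |

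The verdict is first lost at x = 2, 3 and 4 respectively. As a share of enrolled plus excluded patients, it is lost at 1 - 0.85/r: 5.6%, 10.5% and 15.0%.

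**Sensitivity, q = 30%.** The bias is smaller.
- r = 90%: x = 2 gives (18 + 0.6)/22 = 84.5%, still lost.
- r = 95%: x = 3 gives (19 + 0.9)/23 = 86.5%, met; x = 4 gives (19 + 1.2)/24 = 84.2%, lost.
- r = 100%: x = 5 gives (20 + 1.5)/25 = 86.0%, met; x = 6 gives (20 + 1.8)/26 = 83.8%, lost.

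**The same patients counted two ways.** The Figure 3 caption describes a 6-unit exchange with one D+ unit at each of the first two visits. With the one-unit increments of section 4.2 the sequence is 1, 1, 2, 3, 4, 5, 6, or 7 visits. Take 20 patients, 17 always supplied and 3 never. If all are enrolled and followed for 7 visits, the rate is 17 × 7/(20 × 7) = 119/140 = 85.0%, which does not exceed 85%. If the 3 are excluded at screening, it is 119/119 = 100%. Supply is identical in both cases; only the place where the 3 are recorded differs.

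**The case against.** The strongest reply is that a patient known to be unsupplyable cannot usefully be enrolled, that the exclusions are stated openly, and that this is a descriptive single-hospital pilot whose criterion is expressly per study visit. All of that stands as a defence of the exclusions. It does not cover the conclusion: section 6.1 applies a numerical threshold to the strategy as a whole and never says that the answer is conditional on a supply screen. No formal inference is invalidated, because none is planned.

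A reader might infer several stronger things that the documents do not support.

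- *The criterion is bound to be met.* It is not. Section 6.4 provides for considering an individual's termination when their genotype leads to documented delay at three visits in a row, so failures among enrolled subjects are expected to be possible.
- *Only common genotypes and patients with few other antibodies remain.* The criteria remove only needs that rule out supply, which is narrower.
- *The excluded share must be large, since section 1.3 reports variant RH alleles in more than 85% of patients and alloimmunization in 58% of chronically transfused ones.* Neither figure measures unsupplyability. The first counts any variant allele, and section 1.3 says African American donors show a similar degree of variation. The second does not discriminate here, because every patient in the target population already has a history of anti-D.
- *Two or three exclusions always reverse the verdict.* With q from 0 to 30%, that holds throughout only at an observed 90%. At 95%, two exclusions leave 86.4-89.1% and three leave 82.6-86.5%.
- *Every excluded patient is a failure of RH genotype matching.* For item 2 this goes too far. Antigen-negative needs from other antibodies also constrain the standard-of-care units described in section 4.2.
- *All screened patients who meet the inclusion criteria should form the denominator.* That would count refusals, item 3 exclusions and patients left out once recruitment closed at about 20. If the whole pool of 30-40 were screened and met the inclusion criteria, perfect supply would still show only 20/40 to 20/30, or 50-67%.

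**Conclusion.** The structural point holds. Items 1 and 2 select on the quantity that the feasibility objective is meant to measure, and nothing in section 6 restores the excluded patients or narrows the claim. The >85% verdict is conditional on passing a supply pre-screen and is biased upward for the population named in sections 2.1 and 6.1.

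The direction is clear, but the size is not known and cannot be derived from the documents. The thresholds of 2, 3 and 4 exclusions per 20 enrolled, at observed rates of 90%, 95% and 100%, rest on assumed observed rates, equal visits per patient, and counting every excluded patient as wholly unsupplied. If excluded patients could have been supplied at 30% of visits, the thresholds become 2, 4 and 6. These figures show that a handful of patients could decide the verdict in a study of this size; they do not estimate how many will be excluded. Safety conclusions are not affected by this point.

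**What to change.** Leave both exclusions in place as entry rules and change what is counted and claimed.

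1. Keep a prospective screening log of patients who meet every inclusion criterion and are excluded solely under item 1, item 2 or both. Record the genotype or antibody reason and, because the criteria have no cut-off, the basis for judging supply insufficient.
2. In sections 6.1 and 6.2.2, report a supplementary feasibility result beside the visit rate. Its denominator is enrolled subjects plus those logged under step 1. Leave out refusals, item 3 exclusions and patients not enrolled because recruitment had closed. Let each enrolled subject contribute the proportion of their study visits supplied without delay and each excluded patient contribute zero, then average over patients. This avoids assuming equal visits.
3. Show item 1 and item 2 exclusions on separate lines, with any patient meeting both on a third, so that scarcity shared with standard-of-care units can be told apart from scarcity due to RH genotype matching.
4. Word the >85% conclusion as applying to patients who pass the supply pre-screen.

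The cost is small: section 9.4 already screens all chronically transfused patients, so this adds a log, one table and a few sentences. Patients who have not consented can be logged without identifiers. The real downside is a less favourable feasibility figure beside the main one. The log should start with screening, because the denominator may not be recoverable afterwards.

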## **4 STUDY PROCEDURES**

### **4.1 Screening Visit and Baseline Assessment**

The screening visit and baseline assessment will occur on the same day with the following procedures:

[figure not shown]
- Informed consent
- Review inclusion/exclusion criteria
- Demographics/medical history
- Medication review
- Physical exam
- Vital signs
- Laboratory test review
- Medical Record Review

### **4.2 Study Treatment Phase**

Intervention visits will be scheduled with each of the subject's transfusion visits as per the subject's clinical indication for chronic transfusion therapy. We will provide one unit of D+ *RH* genotype matched RBCs at the first transfusion study visit (Figure 3). The remainder of units will be D-, CEK-matched, and negative for all other antigens the patient is alloimmunized

---

against. In this manner, should anti-D be re-stimulated, only one unit of the 3 to 11 units required for red cell exchange will be at risk for hemolysis, and the patient would not become

**Figure 3. Example transfusion protocol for D+ patient with history of anti-D** that is not currently detectable, and requires 6 units per RBC exchange every 3 weeks. One D+ unit will be matched by *RHD* genotype and transfused at the first two study visits, and an increasing number of D+ units will be issued at consecutive RBC exchange visits. U, unit. Triangle denotes a study visit for laboratory studies including an antibody screen, CBC, hemoglobin quantification and bilirubin level

acutely anemic. If laboratory monitoring shows no anti-D re-appearance or signs of increased hemolysis, the patient will receive one unit of D+ *RH* genotype matched RBCs at the 2nd transfusion study visit, and again if no anti-D re-appearance or signs of increased hemolysis, we will increase by one D+ unit per study visit until all units are D+. If a patient re-demonstrates anti-D, we will end that subject's participation and he/she will resume transfusions with D negative RBC units.

All patients with SCD on chronic transfusion therapy have a pre-transfusion complete blood count (CBC), Hgb quantification to determine %hgb A and S levels, and an antibody screen. We will collect a pre-transfusion sample to prospectively store plasma on all study subjects. Patients undergoing chronic red cell exchange will have an immediate post-procedure CBC and hgb quantification as standard of care. Study participants will return 5-12 days post-transfusion for a CBC/reticulocyte count, hgb quantification, bilirubin level, and antibody screen to evaluate for anti-D recrudescence or red cell hemolysis (Table 2).

**Table 2. Laboratory monitoring**

	Pre-transfusion	Immediate Post-transfusion	5-12 days Post-transfusion
Complete blood count	✓	✓	✓
Hemoglobin quantification	✓	✓	✓
Reticulocyte count	✓		✓
Antibody screen/identification	✓		✓
Bilirubin (total, unconjugated)			✓
Creatinine			✓
Plasma sample frozen	✓		✓
Donor red cells frozen	✓		

Any time a patient shows a re-appearance of anti-D on an antibody screen, the medical monitor will be notified, and all safety data will be reviewed. As stated above, if a subject re-demonstrates anti-D, we will end that subject's participation and he/she will resume transfusions with D negative RBC units.

If any subject shows signs of transfused red cell hemolysis, with or without an anti-D identified on the antibody screen, the medical monitor will be notified, and all safety data will be reviewed.

Study stopping criteria include:

- 1) Two of the first 5 enrolled subjects, or after the first 5 enrolled subjects, greater than 30% of enrolled patients, develop re-appearance of anti-D
- 2) Any subject with anti-D re-appearance and clinical or laboratory evidence of transfused red cell hemolysis (dark urine, increased scleral icterus, exacerbated anemia, higher Hb S level than expected based on timing from last transfusion

If either of these criteria occur, the study will be stopped, the safety medical monitor will review all clinical and laboratory evidence to determine safety risks, and will meet with the investigative team to determine a safe course of action. The IRB would be notified and the study procedures would be suspended until approval of the IRB.

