## **3 INVESTIGATIONAL PLAN**

### **3.1 General Schema of Study Design**

There will be a screening and baseline assessment, and a treatment phase. See Table 1 for an overview of the study visits and procedures.

We will enroll at least 5 adults to collect safety and preliminary efficacy data, before enrolling children to the study. The data gathered will be submitted to the IRB via an amendment to be reviewed by the convened board. We will obtain IRB approval before opening enrollment to children.

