## 8 SAFETY MANAGEMENT

### 8.1 Clinical Adverse Events

Clinical adverse events (AEs) will be monitored throughout the study.

We will have a medical monitor independent of the study team who is familiar with SCD and transfusion, and blood bank procedures. The medical monitor will review safety data, including antibody screens for anti-D reappearance, and other laboratory studies, i.e blood counts and hemoglobin quantifications, for signs of transfused red cell hemolysis. Details about the units transfused, including the *RH* genotype, and the red cell antigen profile, will be reviewed.

Any time a patient shows a re-appearance of anti-D on an antibody screen, the medical monitor will be notified, and all safety data will be reviewed. As stated above, if a subject re-demonstrates anti-D, we will end that subject's participation and he/she will resume transfusions with D negative RBC units.

If any subject shows signs of transfused red cell hemolysis, with or without an anti-D identified on the antibody screen, the medical monitor will be notified, and all safety data will be reviewed.

Study stopping criteria include:

- 1) Three of the first 5 enrolled subjects, or greater than 50% of enrolled patients, develop re-appearance of anti-D
- 2) Any subject with anti-D re-appearance and clinical or laboratory evidence of transfused red cell hemolysis (dark urine, increased scleral icterus, exacerbated anemia, higher Hb S level than expected based on timing from last transfusion)

If either of these criteria occur, the study will be stopped, the safety medical monitor will review all clinical and laboratory evidence to determine safety risks, and will meet with the investigative team to determine a safe course of action. The IRB would be notified and the study procedures would be suspended until approval of the IRB.

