### **9.3.2 Risk Assessment**

Risks are greater than minimal. Providing D+ RBC units to a patient with history of anti-D may cause re-appearance of the anti-D with or without transfused red cell hemolysis. *RH* genotype matched red cells provide a higher level of matching, and thus the risk of anti-D reappearing is predicted to be very low. The study was also designed to minimize the risk of harm from anti-D reappearance by transfusing D+ *RH* genotype matched units for only 1 out of a typical 3 to 8 RBC units for the first two visits, and then titrating up by one unit with each subsequent transfusion. There is the possibility that transfusion would be delayed up to 7 days to identify adequate *RH* genotype red cell units, this may cause inconvenience (waiting or rescheduling transfusion visit).

There are risks involved with red cell transfusion, i.e. allergic reaction, infection, alloimmunization, but these risks are associated with routine clinical care and not a result of the research activities.

The risks involved with a venipuncture are pain, bleeding or bruising at the venipuncture site.

---

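### The anti-D stopping rule is given two incompatible sets of thresholds, so the same data suspend the study under sections 4.2 and 9.3.1 but not under section 8.1

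*Combined protocol and SAP*

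**What the plan says.** The study stopping criteria appear three times in the protocol.

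- Section 4.2, after the laboratory monitoring table, and section 9.3.1, the Data and Safety Monitoring Plan, use the same words for the first criterion: "Two of the first 5 enrolled subjects, or after the first 5 enrolled subjects, greater than 30% of enrolled patients, develop re-appearance of anti-D".
- Section 8.1, Clinical Adverse Events, has: "Three of the first 5 enrolled subjects, or greater than 50% of enrolled patients, develop re-appearance of anti-D".

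The second criterion is the same in all three places: "Any subject with anti-D re-appearance and clinical or laboratory evidence of transfused red cell hemolysis". So is the consequence. The study stops, the medical monitor reviews the evidence and meets the investigators, and "The IRB would be notified and the study procedures would be suspended until approval of the IRB".

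On the setting in which the rule operates, section 3.2.2 says "It is expected that approximately 20 subjects will be enrolled to produce 18 evaluable subjects", and section 3.1 says "We will enroll at least 5 adults to collect safety and preliminary efficacy data, before enrolling children to the study". No reappearance rate is given. Section 9.3.2 says only that "the risk of anti-D reappearing is predicted to be very low".

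**The concern.** Since the action is the same in each section, the versions cannot be read as two tiers of response, such as a review trigger and a suspension trigger. They are one rule with two sets of numbers, and nothing says which set prevails.

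The first criterion is the only one that stops the study for anti-D reappearance without hemolysis, and the only one that depends on how many subjects are affected. The versions part at 2 of the first 5 subjects. Those subjects are the adults whose data go to the IRB before children may be enrolled. Someone who looks up the rule in the safety management section would apply a weaker limit than the monitoring plan sets.

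Section 8.1 also leaves out the qualifier that confines the percentage clause to the period after the first 5 subjects. Read literally, one event in the first subject is 100% and stops the study under 8.1, while 4.2 and 9.3.1 would not stop. The versions can therefore also conflict in the opposite direction.

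**Working it through.** The protocol states no stopping probabilities, and its sample size rests on the available patient pool, so there is no figure of its own to reproduce.

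**Inputs from the protocol.** Rule A (sections 4.2 and 9.3.1): at least 2 events in the first 5, then more than 30% of those enrolled. Rule B (section 8.1): at least 3 events in the first 5, or more than 50% of those enrolled. Enrolment is about 20.

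**Step 1: fewest events that stop the study.** At n = 5 the counts are 2 and 3, as written. Beyond that, the minimum is floor(0.30n) + 1 for A and floor(0.50n) + 1 for B. For example, at n = 20: floor(6) + 1 = 7 and floor(10) + 1 = 11.

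| Enrolled | Rule A | Rule B | Counts at which A stops and B does not |
|---|---|---|---|
| 5 | 2 | 3 | 2 |
| 6 | 2 | 4 | 2–3 |
| 10 | 4 | 6 | 4–5 |
| 15 | 5 | 8 | 5–7 |
| 18 | 6 | 10 | 6–9 |
| 20 | 7 | 11 | 7–10 |

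This step needs no assumption about the reappearance risk.

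**Step 2: chance of landing on the disputed result in the first 5.** With a constant risk p, P(exactly 2 of 5) = 10p²(1−p)³. At p = 0.20 this is 10 × 0.04 × 0.512 = 0.205. Over an assumed range it is 2.1% (p = 5%), 7.3% (10%), 20.5% (20%), 30.9% (30%) and 34.6% (40%).

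**Step 3: chance of stopping by 20 subjects.** Let f(n, k) be the probability of reaching n subjects with k events and no stop. Then f(n, k) = (1−p)·f(n−1, k) + p·f(n−1, k−1), and any state that meets the boundary is removed and added to the stopping probability. Rule B is computed in two ways: with the 50% clause starting after subject 5, and with it applied literally from subject 1.

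| Assumed risk | Rule A | Rule B, clause after subject 5 | Rule B, literal |
|---|---|---|---|
| 5% | 3.5% | 0.1% | 5.3% |
| 10% | 13.4% | 0.9% | 11.1% |
| 20% | 45.1% | 7.2% | 25.0% |
| 30% | 76.0% | 22.8% | 42.5% |
| 40% | 93.2% | 47.6% | 63.1% |

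**Assumptions in step 3.** The risks are mine. Each subject's outcome is taken as known before the next subject is counted, and the hemolysis criterion is ignored. The protocol specifies no such staggering, so the table illustrates the gap between the rules and does not predict this study's behaviour.

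**The case against.** The strongest reply is that the conflict is narrow and that a careful reader could manage it. Section 8.1 never authorises continuing at 2 of 5. Someone who applies every listed trigger would stop at the stricter one. Two of the three statements agree, including the monitoring plan, so 8.1 may simply be unrevised text. Other safeguards are the same throughout: one subject with anti-D and hemolysis stops the study, and every reappearance ends that subject's participation and prompts review by an independent medical monitor. The IRB must also approve before children are enrolled, so 2 events in 5 adults could not pass unreviewed into pediatric enrolment.

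Much of this stands, and it limits the problem to anti-D reappearance without hemolysis. It does not remove the problem. No text tells the reader to apply the strictest version or says that 8.1 is out of date. Review by the monitor is not suspension; only the stopping rule imposes that.

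Two points about the numbers also stand. First, the protocol expects a low risk, and at low risks the gap is small in absolute terms. On the literal reading, 8.1 is actually the stricter rule below a risk of about 8% (5.3% against 3.5% at a 5% risk), because of the one-in-one stop. Second, the literal reading is strained: if the 50% clause ran from the first subject, the 3-of-5 clause would be redundant, since 3 events among 5 or fewer subjects always exceed 50%. The reading that starts after subject 5 is the more natural one for 8.1, and it gives the wider gap from 4.2 and 9.3.1.

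**Conclusion.** The concern holds. The current text contains two incompatible versions of a study-level safety threshold, with the same mandatory consequence and no governing section. The event counts alone establish this: 2 of the first 5, or 7 to 10 of 20, suspend the study under sections 4.2 and 9.3.1 and do not meet the anti-D criterion in 8.1. The stopping probabilities show that the difference can be large, at 45% against 7% or 25% for an assumed 20% risk, but they rest on assumed rates and one-at-a-time outcomes. The scope is anti-D reappearance without hemolysis; where hemolysis is present, all sections agree. This should be corrected before the rule has to be used.

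**What to change.** Choose one set of thresholds, state it in full in one place (section 9.3.1 would be natural), and replace the text in the other two sections with a cross-reference. State explicitly whether the percentage clause applies before 5 subjects have been enrolled. The choice of thresholds belongs to the sponsor, the medical monitor and the IRB. If the version in 4.2 and 9.3.1 is the intended one, only section 8.1 needs correcting. It would be useful, though not necessary for the correction, to report the chosen rule's stopping probabilities over a plausible range of reappearance risks.

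The cost is a wording amendment, with no change to sample size, visits or data collection.
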